5.4 Treatment compliance

Novartis will distribute agents direct to sites under individually negotiated contracts. M. D. Anderson Cancer Center (MDACC) will collect and manage regulatory and monitor /audit sites. RAD001 and letrozole will be dispensed from the sites investigational pharmacy. Patients will be provided with an adequate supply (1 cycle plus 1 week) of letrozole plus RAD001 for self-administration at home. Patients are requested to bring their unused medication, including the empty blister packs, to the clinic at each visit. Compliance should be verified by a patient pill diary (Appendix G) and counting the number of tablets consumed between visits.

Records of study medication used, dosages administered, and intervals between visits will be kept during the study, during site visits and at the completion of the trial. Patients

will be asked to return all unused medication at the end of treatment. All unused medication will be returned to the investigational pharmacy.

The site must maintain an overall drug accountability log for the study, as well as individual accountability records (pill diaries) for each patient. The dose, amount dispensed, amount received, and amount unused must be recorded in the source documents for each patient. To avoid waste, leftover medications at the end of each cycle may be used in the subsequent cycle.

5.5 Supportive Care Guidelines/Concomitant Medications

5.5.1 Growth Factors: Routine prophylactic use of growth factors is not permitted. However, therapeutic use in patients with serious hematologic complications such as sepsis may be considered at the investigator's discretion.

[figure not shown]
5.5.2 Antiemetics: The use of antiemetics will be left to the investigator's discretion.

5.5.3 Other Concomitant Medications: In general, concomitant medications and therapies deemed necessary for the supportive care and safety of the patient are allowed, provided their use is documented in the patient record. The administration of any other anticancer agents including chemotherapy and biologic agents is NOT permitted. Similarly, the use of other concurrent investigational drugs is not allowed.

5.6 Drug Information

[figure not shown]
5.6.1 Physical, Chemical and Pharmaceutical Properties of Letrozole

Chemical name:	4,4'-[(1H-1,2,4-triazol-1-yl)methylene]bisbenzotrile
Generic name:	Letrozole
Proprietary name:	Femara [®]
Laboratory code:	CGS 20267
Structural formula:	

Molecular formula:	C ₁₇ H ₁₁ N ₅
Molecular weight:	285.31
Appearance:	White to yellowish, crystalline powder
Melting range:	184-185°C
Hygroscopicity:	Not hygroscopic
Stability:	Very stable
Route of administration:	Oral
Storage conditions:	Do not store above 30°C, protect from moisture.
Shelf life:	5 years

5.6.2 Physical, Chemical and Pharmaceutical Properties of Everolimus

Chemical name:	(1R,9S,12S,15R,16E,18R,19R,21R,23S,24E,26E,28E,30S,32S,35R)-1,18-dihydroxy-12-(1R)-2-[(1S,3R,4R)-4-(2-hydroxyethoxy)-3-methoxycyclohexyl]-1-methylethyl)-19,30-dimethoxy-15,17,21,23,29,35-hexamethyl-11,36-dioxo-4-aza-tricyclo[30.3.1.0 ^{6,9}]hexatriaconta-16,24, 26,28-tetraene-2,3,10,14,20-pentaone
Chemical registry number	159351-69-6
International non-proprietary name	Everolimus
Molecular formula:	C ₅₃ H ₈₃ NO ₁₄
Molecular weight:	958.2
Physical form:	White to faintly yellow powder. Everolimus stabilized with butylated hydroxytoluene (BHT) is amorphous, and contains 0.2% BHT as an antioxidant.
Chirality:	The drug substance, everolimus, contains 15 asymmetric carbon atoms and 4 substituted double bonds. The configuration of the asymmetric carbon atoms and the double bonds are guaranteed by the microbial origin of rapamycin, the starting material of the synthesis, and by the X-ray analysis performed on crystalline everolimus. The configuration at carbon 40 is not changed by the chemical derivatization that converts rapamycin into everolimus.
Formulation:	All formulations are based on an everolimus solid dispersion intermediate that was selected on the basis of the chemical stability of the active ingredient and properties allowing for a good in vivo performance.
Dosage forms:	Tablets: 2.5 mg, 5 mg and 10 mg
Composition/excipients:	Tablets: butylhydroxytoluene/butylated hydroxytoluene (BHT), magnesium stearate, lactose monohydrate, hypromellose/hydroxypropyl methylcellulose, crospovidone, lactose anhydrous The excipients comply with the requirements of the applicable compendial monographs (Ph. Eur., USP/NF).
Stability:	Current stability data permit a shelf life of either 36 months (for 5 mg tablet variants based on solid dispersion dried by evaporation/drying oven) or 24 months (for 2.5 mg, 5 mg and 10 mg tablet variants based on solid dispersion dried by paddle dryer), assuming correct storage below 30°C in the original double sided aluminium blister and protected from light and moisture.

6 STUDY PROCEDURES

Patients will be seen by a physician at the start of treatment and then prior to initiating subsequent cycles, i.e., every four weeks. In order to more precisely determine time of progression, the investigator is encouraged to obtain radiologic assessments earlier if there is a strong clinical suspicion of progression of disease to either confirm or refute the clinical impression. Adverse events will be discussed in detail with each patient and assessed on a continuing basis.

6.1 Schedule of Assessments

Assessments	Screening / baseline	Weekly	Every cycle	Every 2 nd / 3 rd cycle ^d	End of treatment ^j	Follow-up ^h
Medical history	X ^a					
Physical examination	X ^{b,c}		X ^c		X	X
Vital signs	X ^b		X		X	X
Zubrod Performance Status	X ^b		X ^b		X	X
Weight	X ^b		X		X	X
CBC with differential and platelets	X ^b		X		X	
Hepatitis screening/monitoring	X ^{l,n}		X ^{m,o}			
Serum chemistries (Mg+, SGPT, total bilirubin, BUN, serum creatinine/creatinine clearance) and electrolytes, glucose	X ^{b,p}		X		X	
Lipid panel (Triglycerides, LDL, HDL)	X ^b		X		X	
Tumor staging (baseline tumor measurements)	X ^{a,e}					
Chest x-ray	X ^a			X ⁱ	X ⁱ	
CT/MRI of chest, abdomen and pelvis and/or appropriate imaging	X ^{a,e}			X ^f	X ^f	X
Toxicity	X ^a	X ^g	X		X	X
Tumor response				X		
Serum estradiol ^k	X ^a					
Medication compliance/pill count			X ^q			

- a Within 4 weeks prior to Step 2 of study registration (treatment assignment)
- b Within 7 days of initiation of therapy
- c Pelvic exam every cycle if disease is in the pelvis. Otherwise, pelvic exam is done at baseline, after 2 cycles, and then every 3rd cycle thereafter.
- d Obtained after the first two cycles (approximately 8 weeks), after four cycles (approximately 16 weeks) for confirmation, then every three cycles (approximately 12 weeks) thereafter.
- e CT/MRI of chest only in patients with chest disease.
- f Using the same imaging technique used during the initial evaluation.
- g Toxicity will be assessed on an ongoing basis.
- h Follow-up time interval at the physician's discretion. Follow up begins after the patient stops study medication.
- i Only in patients with chest disease
- j Within 4 weeks of the last dose of study drug.
- k Documentation of a serum estradiol < 10 pg/mL is required only for patients in whom hysterectomy was performed premenopausally and in whom bilateral oophorectomy was not completed. Estradiol is not required for women known to be menopausal or surgically castrated.
- l Hepatitis B Virus testing: Prior to randomization (or starting study drug in non-randomized trials), the categories of patients listed in Section 3.2 should be tested for hepatitis B serologic markers and viral load: HBV-DNA HBsAg, HBc Ab, and HBs Ab.
- m HBV DNA monitoring should be done depending on results from serologic markers and viral load as listed in Table 3-3.
- n Hepatitis C Virus testing: Patients with hepatitis C risk factors and additional patients at the discretion of the investigator should be tested for HCV RNA-PCR test at baseline. For a list of hepatitis C risk factors, refer to Table 3-2. Follow-up testing will be performed, as per the visit schedule, only if the patient has a history or is positive at baseline, or both.
- o Patients with detectable HCV RNA-PCR (determined at baseline) and Patients known to have a history of HCV infection, despite a negative viral load test at baseline (including those that were treated and are considered "cured") should be monitored every 4 weeks for HCV reactivation
- p Creatine clearance: Patients must have an adequate renal function of >50cc/min as documented by the Cockcroft Gault formula:
- $$\frac{(140 - \text{age}) \times (\text{weight kg})}{72 \times \text{serum Creatinine (non-IDMS)}} \times 0.85 \text{ (female)}$$
- q Patients are requested to bring their unused medication, including the empty blister packs, to the clinic at each visit. Compliance should be verified by a patient pill diary (Appendix G) and counting the number of tablets consumed between visits.

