Everolimus has immunosuppressive properties and may predispose patients to bacterial, fungal, viral or protozoan infections, including infections with opportunistic pathogens. Localized and systemic infections, including pneumonia, other bacterial infections, invasive fungal infections, such as aspergillosis or candidiasis and viral infections including reactivation of hepatitis B virus, have been described in patients taking everolimus. Some of these infections have been severe (e.g. leading to respiratory or hepatic failure) and occasionally have had a fatal outcome.

Physicians and patients should be aware of the increased risk of infection with everolimus. Treat pre-existing infections prior to starting treatment with everolimus. While taking everolimus, be vigilant for symptoms and signs of infection; if a diagnosis of infection is made, institute appropriate treatment promptly and consider interruption or discontinuation of everolimus. If a diagnosis of invasive systemic fungal infection is made, discontinue everolimus and treat with appropriate antifungal therapy.

Reactivation of Hepatitis B (HBV) has been observed in patients with cancer receiving chemotherapy (Yeo 2004). Sporadic cases of Hepatitis B reactivation have also been seen in this setting with everolimus. Use of antivirals during anti-cancer therapy has been shown to reduce the risk of Hepatitis B virus reactivation and associated morbidity and mortality (Loomba 2008). A detailed assessment of Hepatitis B/C medical history and risk factors must be done for all patients at screening, with testing performed prior to the first dose of everolimus.

Hypersensitivity reactions manifested by symptoms including, but not limited to, anaphylaxis, dyspnea, flushing, chest pain or angioedema (e.g. swelling of the airways or tongue, with or without respiratory impairment) have been observed with everolimus.

Hyperglycemia has been reported in clinical trials. Monitoring of fasting serum glucose is recommended prior to the start of everolimus therapy and periodically thereafter. Optimal glycemic control should be achieved before starting a patient on everolimus. Mouth ulcers, stomatitis and oral mucositis have been seen in patients treated with everolimus. In such cases topical treatments are recommended, but alcohol- or peroxide-containing

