10. Patients must have adequate hepatic function as documented by a serum bilirubin ≤2.5 mg/dL, regardless of whether patients have liver involvement secondary to tumor. Note: A detailed assessment of Hepatitis B/C medical history and risk factors must be done at screening for all patients. HBV DNA and HCV RNA PCR testing are required at screening for all patients with a positive medical history based on risk factors and/or confirmation of prior HBV/HCV infection.
 11. Alanine aminotransferase (SGPT) must be ≤3x institutional upper limit of normal unless the liver is involved with tumor, in that case, the alanine aminotransferase must be ≤5 x institutional upper limit of normal..
 12. Prior to beginning therapy, at least 4 weeks must have elapsed since prior chemotherapy, surgery, radiation therapy, hormonal therapy or investigational therapy. Patients receiving palliative radiation therapy are exempt from the 4 week waiting period.
 13. Baseline lipid levels (triglycerides, cholesterol) must be ≤ grade 1. Patients are allowed to be on lipid lowering drugs.
 14. Patients must be ≥ 18 years of age.

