Registration hours are 8:00 a.m. to 5:00 p.m. Central Standard Time, Monday through Friday, except holidays.

Registration is a 2-step process. Step 1 - Initial registration must be completed:

- After the patient has signed the informed consent and has been determined to be eligible by the local investigator.

Once eligibility has been determined, Step 2 is treatment assignment -

- Before study related treatment is initiated.

At the time of registration the following information will be requested by the MDACC Office of Multicenter Clinical Research (OMCR):

- A faxed or emailed copy of a completed and signed, protocol specific, eligibility checklist form
- One copy of a Pathology report from the patient's most recent surgery or biopsy
- One copy of the signed and dated Informed Consent/Authorization.

The eligibility checklist should be prepared and signed prior to faxing or emailing to the MDACC OMCR. The fax/email should be followed by a phone call to the MDACC OMCR to verify receipt.

If the patient fails eligibility screening do not proceed to the MDACC registration process.

Patient Number for Participating Institutions

Once eligibility has been established during Registration, the patient from the participating institution is assigned a six character MDACC OMCR patient number. This number is unique to the patient and must be written on all data and correspondence for the patient.

Verification of Registration

For participating institutions, a Registration Verification Letter for patients registered will be faxed or emailed to the registering institution within one working day after registration.

Initiation of Therapy

Treatment may not be initiated until the participating institution receives a faxed or emailed copy of the patient's Registration Verification Letter from the MDACC OMCR. Patients must initiate treatment within 10 calendar days after the registration is completed.

The MDACC OMCR must be notified in writing of any exceptions to this policy.

Eligibility Exceptions: Eligibility Exceptions will not be granted.

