5.3.2 Management of Hepatitis reactivation

In cancer patients with hepatitis B, whether carriers or in chronic state, use of antivirals during anticancer therapy has been shown to reduce the risk of hepatitis B virus (HBV) reactivation and associated HBV morbidity and mortality (Loomba et al. 2008).

Monitoring and prophylactic treatment for hepatitis B reactivation

Table 3-2 provides details of monitoring and prophylactic therapy according to the baseline results of viral load and serologic markers testing.

Table 3-2 Action to be taken for positive baseline hepatitis B results

Test	Result	Result	Result	Result	Result
HBV-DNA	+	+ or -	-	-	-
HBsAg	+ or -	+	-	-	-
HBs Ab	+ or -	+ or -	+ and no prior HBV vaccination	+ or -	- or + with prior HBV vaccination
HBc Ab	+ or -	+ or -	+ or -	+	-
Recommendation	Prophylaxis treatment should be started 1-2 weeks prior to first dose of study drug Monitor HBV-DNA approximately every 4 weeks		No prophylaxis Monitor HBV-DNA approximately every 4 weeks		No specific action

Antiviral prophylaxis therapy should continue for at least 4 weeks after last dose of study drug.

For patients who have already received study drug prior to the approval of the amendment, the same process should be followed at the patient's next visit. The first HBV-DNA result would be regarded as baseline.

For hepatitis B reactivation, definition and management guidelines, see Table 3-3 Guidelines for management of hepatitis B.

Table 3-3 Guidelines for management of hepatitis B

HBV reactivation (with or without clinical signs and symptoms)*	

For patients with baseline results: Positive HBV-DNA OR positive HBsAg ----- reactivation is defined as: [Increase of 1 log in HBV-DNA relative to baseline HBV-DNA value OR new appearance of measurable HBV-DNA] AND ALT elevation x 5 ULN
	
Treat: Start a second antiviral AND Interrupt study drug administration until resolution: ≤ grade 1 ALT (or baseline ALT, if > grade 1) and ≤ baseline HBV-DNA levels If resolution occurs within ≤ 28 days study drug should be re-started at one dose lower, if available. If the patient is already receiving the lowest dose of study drug according to the protocol, the patient should restart at the same dose after resolution. Both antiviral therapies should continue at least 4 weeks after last dose of study drug. If resolution occurs > 28 days Patients should discontinue study drug but continue both antiviral therapies at least 4 weeks after last dose of study drug.

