5.3.4 Concomitant therapy

Lipid-lowering drugs

Increased lipid levels are a known adverse effect of treatment with both RAD001 and aromatase inhibitors. In case of hyperlipidemia (\geq grade 1 hypercholesterolemia with or without hypertriglyceridemia), in addition to dietary advice to patients, an HMG-CoA reductase inhibitor such as atorvastatin, pravastatin or fluvastatin may be associated with study treatment.

- It is highly recommended that patients positive HBV-DNA or HBsAg are treated prophylactically with an antiviral for 1-2 weeks prior to receiving study drug (see Section 3.2).
- The antiviral treatment should continue throughout the entire study period and for at least 4 weeks after the last dose of study drug.
- Patients on antiviral prophylaxis treatment or positive HBV antibodies should be tested for HBV-DNA according to study visit schedule.

- Oral contraceptives in preclinical and clinical data have shown everolimus to have CYP3A4 inhibitory activity rather than induction activity, induction of metabolism of contraceptive hormones by everolimus is unlikely. Consequently, administration of everolimus should not reduce the efficacy of oral contraceptives.
- Patients will be provided a list of all drugs/substances to avoid when entered on the study (Appendix E).

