6.2 Screening/Baseline

To be completed within four weeks prior to Step 2 of study registration (treatment assignment):

1. Medical history including list of current medications and dosing schedules, history of previous therapies for current disease; and any residual toxicity from prior therapies should be recorded by using the grading schema in CTCAE, v3.0.
2. Zubrod performance status.
3. Baseline tumor measurements
4. Chest x-ray
5. CT/MRI of chest, abdomen and pelvis and/or appropriate imaging. Chest imaging (only in patients with chest disease)
6. Hepatitis screening

To be completed within seven days of initiation of therapy. Therapy must be initiated within 10 calendar days after Step 2 of registration (treatment assignment):

1. Physical exam including pelvic exam
2. Weight
3. Vital signs (blood pressure, pulse, respiratory rate, temperature)
4. Zubrod performance status
5. Complete blood count with leukocyte differential and platelet count
6. Serum chemistries (magnesium, SGPT, total bilirubin, BUN, serum creatinine, glucose and electrolytes).
7. Lipid panel (Triglycerides, LDL, HDL)

6.3 Treatment Evaluations To be obtained every cycle (4 weeks):

1. Weight
2. Complete blood count, serum chemistries (magnesium, SGPT, total bilirubin, BUN, serum creatinine), glucose and electrolytes.
3. Lipid panel (Triglycerides, LDL, HDL)
4. Vital Signs (blood pressure, pulse, respiratory rate, temperature)
5. Physical exam including pelvic exam every cycle if disease is in the pelvis. Otherwise pelvic exam is performed at baseline, after 2 cycles (8 weeks), and then every 3 cycles (12 weeks) thereafter.
6. Zubrod performance status

7. Assessment of treatment related toxicities
8. Hepatitis monitoring, if indicated
9. Medication compliance, pill count

To be obtained after the first 2 cycles (8 weeks):

1. Evaluation of measurable tumor
2. Physical exam (including pelvic exam)
3. CT/MRI scan of chest, abdomen and pelvis and/or appropriate imaging (the same imaging technique used during the initial evaluation will be performed).
Chest imaging (only in patients with chest disease)
4. Assessment of treatment related toxicities

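### Hepatitis B serology is ordered only for patient categories in a section that does not exist, while inclusion criterion 10 asks for HBV DNA alone

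*Combined protocol and SAP*

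**What the plan says.** Baseline hepatitis B testing is described or assumed in six places.

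- **Section 6.1, footnote l** is the only instruction that orders serology. Before study drug, "the categories of patients listed in Section 3.2 should be tested for hepatitis B serologic markers and viral load"; the footnote then names HBV-DNA, HBsAg, HBc Ab and HBs Ab.
- **Section 4.2, inclusion criterion 10** asks for a history and risk-factor assessment in everyone, then says "HBV DNA and HCV RNA PCR testing are required at screening for all patients with a positive medical history". The positive history may rest on risk factors, on confirmed earlier infection, or on both. No serologic marker is named.
- **Section 1.4.4.2** says that the history and risk-factor assessment "must be done for all patients at screening, with testing performed prior to the first dose of everolimus". It does not say which test is meant, or whether the testing as well as the assessment applies to everyone.
- **Section 5.3.2** explains that "Table 3-2 provides details of monitoring and prophylactic therapy according to the baseline results of viral load and serologic markers testing".
- **Section 5.3.4** strongly recommends that "patients positive HBV-DNA or HBsAg are treated prophylactically with an antiviral for 1-2 weeks prior to receiving study drug (see Section 3.2", which repeats the same pointer. It adds: "Patients on antiviral prophylaxis treatment or positive HBV antibodies should be tested for HBV-DNA according to study visit schedule".
- **Section 6.2** lists hepatitis screening among the assessments for the four weeks before Step 2 of registration, with no marker and no patient group.

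**The concern.** The rule that names the serologic markers does not identify the patients, and the rule that identifies patients does not name the markers. The later safety rules (prophylaxis, monitoring, and the definition of reactivation) all depend on serology results.

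What is at stake is patient safety, not inference. Section 1.4.4.2 reports sporadic hepatitis B reactivation on everolimus, and Section 5.3.2 cites evidence that antivirals reduce that risk. Prophylaxis is meant to begin before the first dose, so a marker that was not drawn at screening cannot be made good once treatment has started.

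**Working it through.** The plan gives no figure to reproduce here. The check is a reading of the hepatitis text side by side.

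**1. Does Section 3.2 exist?** No. The table of contents passes from Section 3 to Section 4 without subsections. Section 3 (Investigational Plan) is one undivided block and does not mention hepatitis. Because the contents list agrees with the body, this is not removed text.

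**2. Would the likely target supply the categories?** The nearest candidate is Section 5.3.2, which holds Table 3-2. It starts from test results and sets actions; it does not say who is tested. Redirecting the pointer there would still leave footnote l without a population.

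**3. Who is tested, and for what?**

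| Place | Patients | Hepatitis B tests |
|---|---|---|
| Footnote l | Undefined (dead pointer) | HBV-DNA, HBsAg, HBc Ab, HBs Ab |
| Inclusion 10 | Positive history and/or confirmed prior infection | HBV DNA |
| Section 1.4.4.2 | Possibly all patients | Not named |
| Section 6.2 | Not stated | Not named |

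No row gives both a defined group and the serologic markers.

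**4. What does a negative HBV-DNA result leave open?** Under Table 3-2, an HBV-DNA-negative patient falls into one of three groups, separated only by serology:

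| Serology when HBV-DNA is negative | Action in Table 3-2 |
|---|---|
| HBsAg positive | Prophylaxis from 1-2 weeks before first dose; HBV-DNA about every 4 weeks |
| HBsAg negative, and HBc Ab positive or HBs Ab positive without vaccination | No prophylaxis; HBV-DNA about every 4 weeks |
| HBsAg and HBc Ab negative, HBs Ab negative or explained by vaccination | None |

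Criterion 10 guarantees only the DNA result, which cannot tell these groups apart.

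**5. Does the gap carry forward?** Yes. Section 5.3.4 makes on-study HBV-DNA testing depend on prophylaxis or antibody status, so a patient with no serology would not be scheduled for it. Table 3-3 also needs serology for a DNA-negative patient. If HBsAg is positive, reactivation requires new HBV-DNA together with ALT elevation at 5 times the upper limit of normal. If HBsAg is negative and an antibody is positive, new HBV-DNA alone is enough.

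**6. Upper bound on added tests.** Section 10 caps the trial at 42 patients. Criterion 10 would gain 3 markers, so at most 42 x 3 = 126 marker tests among enrolled patients, if every one of them were tested. Anyone screened but not enrolled would add up to 3 more.

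**The case against.** **The rules can be read together.** Criterion 10 gives a population, footnote l gives a panel, and a site can comply with both. This stands. A reader might infer that the two contradict each other, or that the plan omits serology altogether; the documents support neither. What is missing is the written link. Section 1.4.4.2 also permits a wider reading, testing of all patients, so two sites could reasonably settle on different groups.

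**A site would notice.** Table 3-2 cannot be applied in full without HBsAg and the antibodies, and the schedule attaches footnote l to hepatitis screening. This lowers the risk but does not remove it. Table 3-2 is titled as dealing with positive baseline results, so a site holding one negative DNA result has no clear prompt to open it.

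**SGPT is measured every cycle in all patients.** This is a partial backstop, because ALT is part of the reactivation definition for DNA- or HBsAg-positive patients. It acts only after dosing has begun, so it does not replace prophylaxis. It also does not cover the antibody-only group, whose reactivation is defined by HBV-DNA alone.

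**Sites also use an eligibility checklist that is not among the documents** (Section 5.1). It may or may not specify serology. Footnote l does not refer to it.

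**Timing.** A reader might infer that the registration window rules out prophylaxis, since "Patients must initiate treatment within 10 calendar days after the registration is completed". It does not. With dosing by day 10 after Step 2, a 7-day course must start by day 10 - 7 = 3, and a 14-day course by day 10 - 14 = -4, that is, 4 days before Step 2. Screening opens four weeks before Step 2, so both are feasible.

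**Conclusion.** The point holds as a gap in safety screening that should be closed by amendment. Footnote l is the only order for HBsAg, HBc Ab and HBs Ab, and its population is undefined. Criterion 10, the clearest rule a site can carry out, yields less information than Table 3-2 needs. Followed literally, it could let a patient start everolimus without the prophylaxis or the monitoring that the plan itself calls for.

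The number of patients affected is unknown, because the documents give neither the prevalence of hepatitis B markers nor the share of patients with a positive history. Counting marker combinations in Table 3-2 would not help: such counts depend on how the table is coded and are not patient frequencies.

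The conclusion assumes that a site may act on criterion 10 alone and that the unseen checklist does not already require serology. It has no bearing on the sample size, stopping rule or primary analysis.

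Other references are also loose. Section 5.3.4 repeats the dead pointer. Footnote m cites Table 3-3 although the four-weekly rule is in Table 3-2, which is arguable because Table 3-3 also sorts patients by baseline results. Footnote n cites Table 3-2 for hepatitis C risk factors that it does not list. These are clerical and add nothing to the weight of the point.

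**What to change.** Amend inclusion criterion 10 to require HBV-DNA, HBsAg, HBc Ab and HBs Ab at screening, before the first dose, at least in the population it already defines. Results should be available early enough for 1-2 weeks of prophylaxis where Table 3-2 calls for it. Replace footnote l's reference to Section 3.2 with a reference to criterion 10. If the sponsor meant all patients to be tested, as Section 1.4.4.2 can be read, criterion 10 should say so; the documents do not settle which was intended. The clerical pointers can be corrected in the same amendment.

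The cost is amendment wording plus three blood markers per tested patient, all already named in footnote l. No new visit is needed, because Section 6.2 already places hepatitis screening in the four weeks before Step 2.
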